5.2. Endpoints

5.2.1. Primary Endpoint

The percentage of subjects with “complete response (CR),” defined as complete eradication of squamous histological abnormalities (MGIN or worse) within the treatment area (TA) at 12 months after the initial treatment session (per protocol analysis). Patients who show ESCC in biopsies or resection samples are defined as failures for this endpoint, even if subsequent biopsies at 12 months indicate CR. The primary study hypothesis is that 80% of treated subjects will have a complete response.

Patients

All 100 patients who are included in the cohort will be assessed for the primary endpoint. The run-in patients will not be included for the primary endpoint analysis.

Biopsies

Only biopsies obtained from the original USL bearing portion of the esophagus (the treatment area) will be used in the analysis for the primary endpoint analysis. MGIN or worse noted in any biopsy from outside this region are not considered failures of ablation for the purposes of the primary endpoints.

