In the very unlikely scenario that any biopsy subsequently shows MGIN+ despite a normally stained esophagus, the entire TA is treated once again with circumferential or focal RFA (to ensure complete treatment of any occult neoplasia.)

Scenario #2: USLs are present in the TA

If there are **residual flat USLs within the original TA**, the investigator records the extent of the USLs (length, diameter, location) and obtains biopsies of each USL starting distally and moving proximally as follows:

For each two centimeters in length, 1 level of biopsies will be performed. The number of biopsies per level depends on the circumferential extent of the USL as follows:

- <25% of circumference: 1 biopsy per level
- 25 – 49% of circumference: 2 biopsies per level
- 50 – 74% of circumference: 3 biopsies per level
- ≥75% of circumference: 4 biopsies per level.

Example: for a USL of 3 centimeter in length covering 60% of circumference, 2 levels with 3 biopsies per level will be performed, summing up to a total of 6 biopsies.

Each set of unique USL samples are placed in individual containers, and labeled as to their location. If 3 or more biopsies are obtained from a single USL, use multiple jars for that USL with a maximum of 2 biopsies per jar. The investigator designates the staining characteristic of each tissue area prior to biopsy, and enters this information on the Table of findings CRF. It is presumed that biopsies from USLs are unstained, while biopsies from the non-USL TA are "stained". The CRF also contains information about each specimen/USL location.

Treatment of USL

In general, all residual flat USLs during follow-up will be treated with RFA.

USLs that are deemed clearly reactive can be biopsied without need for additional treatment. Clearly reactive USLs will be defined as any USL with stain code III (lightly stained) that is deemed as non-suspicious for ESCN and reactive after RFA on both WLE and NBI by the Investigator. If a USL will be deemed reactive and therefore left untreated, and if subsequent biopsies do show MGIN or worse, the USL will then be treated on the next endoscopy, independent of the endoscopic appearance.

If subsequent biopsies show cancer, patients is defined as progressor will be considered a failure for the primary endpoint and he will be offered escape treatment (see section 9.4.3. for description), at the discretion of the physician under the hospital standard of care.

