If any **non-flat USL (Paris type 0-I, 0-IIa, 0-IIc, 0-III)** is detected, independent of its staining characteristics upon Lugol's staining, or WLE, NBI or Lugol's chromoendoscopy show a lesion suspicious for ESCC (e.g. 'pink sign' USL, defined as a color change after Lugol's staining: initially whitish yellow and pink 2-3 minutes later), or if previous biopsies from this lesion showed ESCC, subject will be managed with escape treatment (see section 9.4.3 for description), at the discretion of the physician under hospital standard of care depending on the lesion type. If histology is needed before

escape treatment, a keyhole biopsy should be performed, but the Investigator can perform escape treatment if deemed necessary, regardless of the biopsy result. The patient will be considered a failure for the primary efficacy endpoint only if escape treatment histology shows progression to ESCC. If histology does not show ESCC, the patient will return in 3 months from escape treatment for possible RFA and will be eligible for success in the primary endpoint. For continuation on trial, please refer to section 9.4.3.

Scenario #4: USLs are present outside the TA

If any **new USL(s) is (are) detected outside the TA** during follow-up prior to 12 months, it is biopsied and the biopsy fragments are placed in a separate container and labeled as to their location. This finding does not alter the plan for RFA inside TA for that particular procedure, and the USL outside the TA is treated according the standard practice under hospital standard of care.

During all endoscopies, re-tattoos will be performed if necessary. If clinically indicated, extra endoscopies can always be performed.

12 Months Follow-up Endoscopy

No RFA is provided to any subject at the 12-month primary endpoint biopsy visit.

For the biopsy methodology for the primary endpoint:

1. If there are no USLs within the TA, see Section 10.4, "Scenario #1: No USLs are present"
2. If there are one or more persistent USLs within the TA, see Section 10.4, "Scenario #2: USLs are present"

If there are any USLs discovered outside the original USL bearing esophagus, these may be biopsied or resected, but must be submitted in separate containers are not considered in the primary endpoint analysis.

Patients with a CR at 12 months will enter the follow-up phase as described in figure 2 and section 9.4.2.

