- If the disease stage exceeds the limits for endoscopic treatment (i.e.: either one of: poor differentiation, positive vertical resection margins, sm-2 or sm-3 invasion or lymphovascular invasion), patient will be considered a failure for the primary endpoint. The Investigator will decide which escape treatment to perform, and the patient will be followed to study termination for assessment of secondary endpoints.
 - If histology does not demonstrate ESCC, patient will remain eligible for inclusion as a success in the primary and secondary endpoints. The application of RFA after endoscopic resection may be performed after minimally 8 weeks later.

Discharge Instructions after RFA Procedures

- Liquid acetaminophen with narcotic per oral as needed for pain
- Liquid antacid, lidocaine, and sucralfate slurry or Almagate Suspension for first 5 days, as needed
- Liquid diet for 3 days, then soft diet for 4 days, then normalize
- At the direction of the physician, anti-thrombotic agents should be avoided for 7 days before and after any RFA procedure.
- All patients commence proton pump inhibitor (PPI) medication (esomeprazole 40 mg bid) after the Primary RFA to allow restoration of a normal epithelium. Patients will continue PPI after each RFA session until endoscopy and biopsy demonstrate no further MGIN+ and no need for further RFA.
- Contact physician for any vomiting, shortness of breath, pain not controlled on medication, fever, or bleeding.
- Subject is educated to not eat very hot foods including soups, and not drink very hot liquids as such behavior can delay healing and potentially promote stricture formation and prolonged pain. Subject is instructed to not eat or drink anything in which they are unable to comfortably place their finger for at least 10 seconds prior to ingesting.

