9.10. Definitions

-CR = complete response

Absence of MGIN or worse in biopsies from TA at a single endoscopy.

- Escape treatment

Escape treatment is indicated for lesions with (i) ESCC in biopsies, (ii) non-flat lesions, or (iii) lesions otherwise suspicious for ESCC (e.g. pink-sign positive lesions). Escape treatment will be performed by investigator's distinction and per hospital's standards of care. Subsequent pathology assessment determines whether patient is defined as progressor and failure for the efficacy endpoint.

- Progressive disease

This term is applicable during the whole study. Progressive disease is defined as ESCC in any biopsy or resection specimen. Progressive disease on biopsy will always be treated with escape treatment.

Patients with progressive disease within the first 12 months are a failure for the primary efficacy endpoint, whereas progression patients in subsequent 4 years of follow-up are a failure for the durability endpoint. Progressive disease can be classified into 2 categories based on pathology:

- Eligible for endoscopic treatment, if all of the following characteristics are met: good to moderate differentiation, negative vertical resection margins, m1/m2/m3/sm1 disease and without lymphovascular infiltration.
- Exceeding the limits for endoscopic treatment, if any of the following characteristics was found: poor differentiation, positive vertical resection margins, sm-2 or sm-3 invasion or lymphovascular invasion.

- Treatment failure

This term is applicable to the first 12 months of study. All patients with residual ESCN at the 12 months endoscopy, and patients who progressed to ESCC before 12 months, will be defined as treatment failures.

- Sustained CR

This term is applicable during follow-up, to all patients that were not defined as treatment failures at 12 months. Sustained CR is defined as sustained eradication of MGIN or worse in biopsies from TA, during all FU endoscopies until 60 months.

- Recurrent disease

This term is applicable during follow-up, to all patients that were not defined as treatment failures at 12 months. Recurrent disease is defined as flat (Paris type 0-IIb) USLs with MGIN or HGIN in biopsies from TA during FU, independent of baseline pathology. Recurrent disease will be treated with RFA initially, or escape treatment if persistent, as described in section 9.4.3

10. Risks and Benefits

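### Scenario #3 and section 9.4.3 keep a subject with ESCC on biopsy eligible as a primary success if the endoscopic resection specimen is clear, against the endpoint definition in 5.2.1

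*Protocol*

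**What the plan says.** **Places that make biopsy ESCC a failure.** CIP 5.2.1 and SAP 7.9.1 use the same words: "Patients who show ESCC in biopsies or resection samples are defined as failures for this endpoint". Both add that a clear set of biopsies at 12 months does not reverse this. Scenario #2 in CIP 9.4.1 agrees: "If subsequent biopsies show cancer, patients is defined as progressor will be considered a failure for the primary endpoint". CIP 9.10 gives the definition, "Progressive disease is defined as ESCC in any biopsy or resection specimen", and its consequence, "Patients with progressive disease within the first 12 months are a failure for the primary efficacy endpoint". The Synopsis also defines progression by any biopsy or resection specimen and calls it a primary failure.

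**Places that let the later specimen decide.** Scenario #3 in CIP 9.4.1 covers non-flat lesions, lesions suspicious for ESCC, and a third group: "or if previous biopsies from this lesion showed ESCC". For all of them it says: "The patient will be considered a failure for the primary efficacy endpoint only if escape treatment histology shows progression to ESCC". If that histology shows no ESCC, the subject stays eligible for primary success. In CIP 9.4.3, the last bullet on endoscopic treatment reads: "If histology does not demonstrate ESCC, patient will remain eligible for inclusion as a success in the primary and secondary endpoints". The same section lists ESCC in biopsies as an indication for escape treatment and labels it progression.

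**One place that can be read either way.** The escape-treatment entry in CIP 9.10 ends: "Subsequent pathology assessment determines whether patient is defined as progressor and failure for the efficacy endpoint".

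**The concern.** The primary result is a single proportion from an open, single-arm trial, so each subject needs one unambiguous outcome. Here the procedures section and the endpoint section give opposite outcomes to the same subject.

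The protocol's own procedures can produce such a subject. Under Scenario #2 a flat unstained lesion is biopsied and, in general, ablated at the same session. If the biopsy result then comes back as ESCC, Scenario #2 makes the subject a failure. At the escape-treatment visit the lesion enters Scenario #3 through its earlier biopsy. It has by then been ablated, so a resection specimen without ESCC is plausible. Scenario #3, followed as written, would then allow a subject with histological cancer to be reported as a complete response.

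**Working it through.** **1. Same subject, each rule.** Take a subject with ESCC on a treatment-area biopsy at month 3, 6 or 9, then EMR or ESD with no ESCC in the specimen, then no MGIN or worse in the treatment area at 12 months.

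| Source | Primary outcome |
|---|---|
| CIP 5.2.1; SAP 7.9.1 | Failure |
| Synopsis, study procedures | Failure |
| CIP 9.4.1, Scenario #2 | Failure |
| CIP 9.10, progressive disease | Failure |
| CIP 9.4.1, Scenario #3 | Eligible for success |
| CIP 9.4.3, last histology bullet | Eligible for success |
| CIP 9.10, escape treatment | Unclear |

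**2. Who is affected.** All four conditions must hold:
- ESCC on biopsy before month 12. Without it the rules agree.
- Endoscopic escape treatment. Non-endoscopic therapy is a primary failure under 9.4.3 in any case.
- No ESCC in the specimen. Otherwise both rules give failure.
- No MGIN or worse in the treatment area at 12 months. Otherwise the subject fails anyway.

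**3. The plan's precision, for scale.** CIP 13.2 and SAP section 6 state a 95% half-width of 6%-8% for n=100 and a CR rate of 80%-90%. With 1.96 × √(p(1−p)/n):
- p = 0.80: 1.96 × √(0.80 × 0.20/100) = 7.84%
- p = 0.90: 1.96 × √(0.90 × 0.10/100) = 5.88%

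The stated figure reproduces.

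**4. Size per subject.** The shift is 1/n. At n=100 it is 1.0 point. The per-protocol set may be smaller: at the 3% and 20% dropout figures in CIP 13.2 it is 1/97 = 1.03 and 1/80 = 1.25 points.

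**5. Illustration.** The count k of affected subjects is an assumption, because the documents give none. The starting value of 82/100 is also an assumption, taken from the 82% CR rate that CIP 6.2 reports for the same primary regimen in 17 patients. Intervals are exact (Clopper-Pearson).

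| k | CR if 5.2.1 is applied | 95% CI |
|---|---|---|
| 0 | 82% | 73.1%-89.0% |
| 1 | 81% | 71.9%-88.2% |
| 2 | 80% | 70.8%-87.3% |
| 3 | 79% | 69.7%-86.5% |

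From this starting value, three subjects would take the point estimate below the hypothesised 80%. A shift of 1 to 3 points stays well inside the 6-8 point half-width.

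**The case against.** The strongest reply is that Scenario #3 is headed as dealing with suspicious lesions. Its restriction follows a sentence allowing escape treatment whatever the biopsy shows, and its evident purpose is that resecting a merely suspicious lesion should not by itself count as failure. On this view a subject with cancer on biopsy has already failed under Scenario #2 before Scenario #3 applies. The purpose is credible, but the wording does not carry it: the entry condition names lesions with ESCC on an earlier biopsy, and the scoring sentence makes no exception for them.

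Other parts of the reply stand:
- **The analysis plan is not split.** A reader might infer that the sponsor is free to choose the rule once specimens are read. The SAP states only the any-biopsy rule and contains nothing of Scenario #3, so an analyst following it scores this subject a failure. The SAP was, however, written for CIP v4 while the protocol is v7.0, and neither document says which text prevails.
- **Secondary endpoint 3 is not itself contradictory.** A reader might infer that progression within 12 months is equally undefined. Its definition in CIP 5.2.2 and SAP 7.9.2 plainly counts ESCC in a biopsy or a resection specimen within the treatment area. Scenario #3 speaks only of the primary endpoint. What blurs it is the mention of secondary endpoints in the 9.4.3 bullet.
- **The escape-treatment entry in 9.10 is weak evidence of conflict.** The Synopsis uses nearly the same phrase and defines progression by any biopsy or resection specimen, so the entry can be read consistently with 5.2.1.
- **Over-read biopsies are partly covered.** CIP 9.1.1 requires two independent readings, with consensus, for specimens of progressive disease, including biopsies. Table 2, however, does not tick the second pathologist at months 3, 6 or 9.

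**Conclusion.** Wrong as written: this is an internal contradiction in the scoring of the primary endpoint. Scenario #3 and the last histology bullet of 9.4.3 conflict with 5.2.1, the Synopsis, Scenario #2, the progressive-disease definition in 9.10 and SAP 7.9.1.

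The effect is limited to subjects who meet all four conditions above. Their number is not given and may be zero. A reader might infer a shift of several points in CR or a large relative change in endpoint 3. The documents give no basis for such counts, and the endpoint 3 change would also require that endpoint to ignore its own definition.

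It should be fixed before pathology is scored. It is not graver than that, because the SAP already states the any-biopsy rule.

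**What to change.** The change concerns outcome classification only; no treatment rule is touched. Make 5.2.1 the single scoring rule and carry it through:

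1. **CIP 9.4.1, Scenario #3:** score primary failure if ESCC is found in any biopsy or resection specimen from the treatment area.
2. **CIP 9.4.3, last histology bullet:** make continued eligibility as a success depend on neither biopsies nor resection histology demonstrating ESCC. This also clears up the reference to secondary endpoints.
3. **CIP 9.10, escape treatment:** clarify that the pathology assessment means any biopsy or resection specimen, as in the Synopsis.
4. **CIP 9.1.1 and Table 2:** state that the two-reader consensus applies to any biopsy read as ESCC at months 3 to 9, and mark it in the table.
5. **Reporting:** list subjects with ESCC on biopsy that was not confirmed in the specimen.

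The cost is a few wording changes and a second reading of any ESCC biopsy at months 3 to 9, which 9.1.1 already implies. Sample size, visits and stated precision do not change. The downside is that the CR rate may be slightly less favourable than under Scenario #3 as written.

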9.4.2. Follow-up Phase

All subjects with a CR at 12 months will immediately enter follow-up phase. All patients with residual ESCN at 12 months who achieve CR upon endoscopic escape treatment will also enter the follow-up phase. All patients who progress to ESCC and require escape treatment during the trial, including non-endoscopic, will enter the follow-up phase regardless of primary endpoint failure to assess secondary endpoints. All endoscopies in the follow-up phase will be observed by an expert from CICAMS.

Follow-up procedures include (fig 2):

Annual follow-up endoscopy visit:

- upper endoscopy
- re-tattoo the TA, as necessary
- stain the esophagus with Lugol's solution
- map the entire esophagus for USLs

For TA:

- i. If no USLs in TA, perform biopsies of TA (2 biopsy specimens are obtained for every 2cm segment of the original USL-bearing esophageal segment)
- ii. If unstained lesion (USLs) are found in the TA, each lesion will be biopsied (as described in section 9.4.1, scenario #2). In addition, 2 biopsy specimens are obtained for every 2cm segment of the original USL-bearing esophageal segment that does not now contain USLs. All flat USLs will be treated with RFA. One exception needs to be addressed in line with the treatment phase: clearly reactive USLs may be biopsied and left untreated.
- iii. Any non-flat lesion or lesion suspicious for ESCC (e.g. 'pink sign') in TA will be treated with escape treatment (see section 9.4.3 for description), at the discretion of the physician under hospital standard of care.
- iv. Subsequent follow-up will be determined by pathology results:
 1. If biopsies show LGIN or less: next follow-up endoscopy will occur in a year.
 2. If any biopsies are found to have MGIN or HGIN, endoscopy with RFA will be repeated at 3 month intervals until resolution of MGIN or HGIN is demonstrated. If patient still harbors MGIN or HGIN after a maximum of 4 consecutive 3-monthly RFA sessions, escape treatment will be performed.
 3. If ESCC is found in any biopsy, the patient will be treated with escape treatment.

Outside the TA:

- v. If no USLs, biopsies will not be necessary
- vi. If USLs are found outside the TA, each lesion should be biopsied and treated per investigator's discretion.

1. If any biopsies from outside the TA are found to be MGIN or worse, patient will be treated and followed-up at the discretion of the physician under hospital standard of care.
- Central pathology review of biopsies for all biopsies or resection specimens during FU, with independent reading from two pathologists in case of recurrent or progressive disease.
 - Safety assessment

If clinically indicated, Investigator may always perform extra endoscopies in addition to figure 2.

9.4.3. Escape treatment: Endoscopic (EMR or ESD) or Non-Endoscopic Therapy during Treatment or Follow-up Phase

Several indications for escape treatment exist:

[figure not shown]
- Any non-flat lesion (Paris type 0-I, 0-IIa, 0-IIc, 0-III) during treatment or follow-up phase
- Any abnormality under WLE or Lugol's chromoendoscopy that is suspicious for ESCC (e.g. 'pink sign' USL, defined as a color change after Lugol's staining: initially whitish yellow and pink 2-3 minutes later)
- ESCC in biopsies during treatment or follow-up phase (defined as progression of disease)
- Presence of MGIN or worse in any biopsies from TA at the 12 months endoscopy
- Persistent MGIN or worse during follow-up phase despite a maximum of 4 consecutive 3-monthly RFA sessions
- If clinically indicated per Investigator's discretion

Escape treatment can be performed endoscopically (EMR or ESD), or non-endoscopically (surgery, radiotherapy or chemotherapy) per investigator's discretion under the hospital's standards of care. All patients, regardless of treatment used or failure of the primary endpoint, will be followed to study termination for assessment of secondary endpoints:

- Patients who undergo non-endoscopic therapy will be considered a failure for the primary endpoint, but will be tracked through the 5-year follow-up to assess secondary endpoints.
- For patients who undergo endoscopic treatment, final pathology is required:
 - If the disease stage is eligible for endoscopic escape treatment (i.e.: good to moderate differentiation and negative vertical resection margins and m1/m2/m3/sm1 disease and without lymphovascular infiltration), further treatment and/or follow-up endoscopies after the escape treatment will occur according to

Medtronic Confidential

- the study protocol. The application of RFA after endoscopic resection may be performed after minimally 8 weeks later.
- If the disease stage exceeds the limits for endoscopic treatment (i.e.: either one of: poor differentiation, positive vertical resection margins, sm-2 or sm-3 invasion or lymphovascular invasion), patient will be considered a failure for the primary endpoint. The Investigator will decide which escape treatment to perform, and the patient will be followed to study termination for assessment of secondary endpoints.
 - If histology does not demonstrate ESCC, patient will remain eligible for inclusion as a success in the primary and secondary endpoints. The application of RFA after endoscopic resection may be performed after minimally 8 weeks later.

Discharge Instructions after RFA Procedures

- Liquid acetaminophen with narcotic per oral as needed for pain
- Liquid antacid, lidocaine, and sucralfate slurry or Almagate Suspension for first 5 days, as needed
- Liquid diet for 3 days, then soft diet for 4 days, then normalize
- At the direction of the physician, anti-thrombotic agents should be avoided for 7 days before and after any RFA procedure.
- All patients commence proton pump inhibitor (PPI) medication (esomeprazole 40 mg bid) after the Primary RFA to allow restoration of a normal epithelium. Patients will continue PPI after each RFA session until endoscopy and biopsy demonstrate no further MGIN+ and no need for further RFA.
- Contact physician for any vomiting, shortness of breath, pain not controlled on medication, fever, or bleeding.
- Subject is educated to not eat very hot foods including soups, and not drink very hot liquids as such behavior can delay healing and potentially promote stricture formation and prolonged pain. Subject is instructed to not eat or drink anything in which they are unable to comfortably place their finger for at least 10 seconds prior to ingesting.

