If an indication for additional RFA exists, the investigator will determine whether to provide secondary RFA with the circumferential or focal device, based on the extent of disease:

- If lesions involve more than 3/4 of the circumference, circumferential RFA will be used
- If lesions involve less than 3/4 of the circumference, focal RFA will be used
 - It is presumed that all secondary RFA procedures will be performed with the focal device, and this presumption is reflected in Figure 1.

If focal RFA is selected, it is important to note that the effect of Lugol's may significantly wane during the biopsy procedures therefore it may be necessary to reapply the Lugol's in order to target the remaining USLs. Or simply use the biopsy sites for targeting. Each USL is treated so that the ablation effect overlaps at least 5 mm onto the normal staining esophageal mucosa surrounding the USL. The energy density setting is 12 J/cm² and the power density setting is 40 W/cm². Each USL is ablated 3x without changing the position of the catheter. Upon completing focal RFA of USL(s), biopsies are obtained from the TA avoiding all acute RFA sites. Two biopsy fragments are obtained from every 2 cm of the original USL-bearing esophagus that was not treated at this session (see Figure 1).

Example: TA from 30-40, USL bearing esophagus 31-39. One USL at 3 months from 31-32. Sample USL, then RFA USL. Then obtain 2 biopsy fragments from every 2 cm starting at 33-35, 35-37, and 37-39 cm. The area of the USL is avoided (31-33 cm).

In the unlikely event that circumferential RFA is selected for a follow-up RFA, the entire extent of original TA is treated, using same technique as at the primary RFA session.

If necessary, a maximum of four RFA sessions will be performed in total for each patient in this study. If USLs with MGIN or worse in the TA persist after four sessions, the subject is considered a failure for the primary endpoint. Such patients will undergo escape treatment.

Scenario #3: Lesions Suspicious for ESCC Are Present in the TA

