Patients with residual ESCN at 12 months will be defined as treatment failures, and will undergo escape treatment within 3 months (+/- 4 weeks). If CR will be re-established after escape treatment, patients will stay in the trial and will be followed-up and treated if necessary, according to figure 2. If non-endoscopic treatment is performed at 12 months, or if pathology indicates non-endoscopic treatment, patients won't be treated and/or followed-up according to the study protocol, but will still be followed-up until 5 years after baseline to assess secondary endpoints.

[figure not shown]

Figure 1. Decision Tree for Subject Flow Through in Treatment Phase (adapted from He et al., 2014 (18))

[figure not shown]

Figure 2. Decision Tree for Subject Flow in Follow-Up Phase (adapted from He et al., 2014 (18))

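### The planned breakdown by escape treatment has no time window, so 12-month failure can itself define the group; and no planned figure shows the 12-month CR reached without resection

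*Protocol*

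**What the plan says.** **Who can count as a success.** The primary objective (CIP 5.1.1, SAP 4.1) concerns the effectiveness of the RFA system at 12 months. CR is defined by histology at one endoscopy (CIP 9.10), whatever treatment came before. For lesions suspicious for ESCC in the treatment area (TA), CIP 9.4.1 Scenario #3 says "The patient will be considered a failure for the primary efficacy endpoint only if escape treatment histology shows progression to ESCC". CIP 9.4.3 agrees: "If histology does not demonstrate ESCC, patient will remain eligible for inclusion as a success in the primary and secondary endpoints".

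**Who is already a failure.** ESCC in any biopsy or resection sample is a failure (CIP 5.2.1). So are:
- persistent disease: "If USLs with MGIN or worse in the TA persist after four sessions, the subject is considered a failure for the primary endpoint" (CIP 9.4.1 Scenario #2);
- non-endoscopic escape treatment: "Patients who undergo non-endoscopic therapy will be considered a failure for the primary endpoint" (CIP 9.4.3);
- disease beyond the limits for endoscopic treatment (CIP 9.4.3).

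**What happens to 12-month non-responders.** Under the 12-month heading of CIP 9.4.1, patients with residual ESCN "will be defined as treatment failures, and will undergo escape treatment within 3 months". CIP 9.4.3 lists as an indication for escape treatment: "Presence of MGIN or worse in any biopsies from TA at the 12 months endoscopy".

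**What is planned.** CIP 13.6 lists escape treatment beside study center, age, gender and disease severity as a subgroup factor, with no time limit. SAP 7.11 has the same list without it. Secondary endpoints 8 and 9 separate durability with RFA from durability with RFA plus EMR or ESD, but only after month 12. The planned sensitivity analyses cover discontinuations and missing data only (CIP 13.6, SAP 7.4).

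**The concern.** There are two linked gaps.

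First, a confounder is normally something fixed before treatment. Escape treatment follows treatment, and in part follows the endpoint itself. If a patient enters the escape group because the 12-month biopsy showed MGIN or worse, the subgroup sorts patients by outcome. CR without escape treatment is then pushed towards 100%, and a reader could take this as evidence about RFA alone.

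Second, the group that can be resected before month 12 and still succeed is narrow: mainly non-flat or suspicious lesions that prove not to be ESCC, plus resections at the investigator's discretion. Counting them answers a question about RFA with endoscopic rescue allowed. The objective is worded for the RFA system, and the plan makes the RFA-versus-resection split for durability but not for the primary endpoint. A reader of the 12-month result could not tell whether rescue contributed to it.

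**Working it through.** **1. The plan's own figure.** CIP 13.2 and SAP 6 state a half-width of 6% to 8% for 100 subjects at 80% to 90% CR. With 1.96 × √(p(1−p)/100), p = 0.80 gives 7.84 points and p = 0.90 gives 5.88. The figure reproduces.

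**2. The breakdown with no time window.** Take 100 patients, 80 CR and 20 non-CR (the low end of the plan's expected range). Let k be CR patients resected before the 12-month biopsy and L be CR patients given escape treatment in years 2 to 5. Both are assumptions. Suppose, as CIP 9.4.1 and 9.4.3 read, that all 20 non-CR patients receive escape treatment.

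- CR without escape = (80−k−L)/(80−k−L) = 100% for any k and L.
- CR with escape = (k+L)/(k+L+20).

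| k | L | Without escape | With escape |
|---|---|---|---|
| 0 | 0 | 80/80 = 100% | 0/20 = 0% |
| 3 | 0 | 77/77 = 100% | 3/23 = 13.0% |
| 5 | 5 | 70/70 = 100% | 10/30 = 33% |

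The contrast is present even when k = 0. In the last row, the responders without escape treatment number 70 of 100, while the 12-month CR with early resection as non-response is (80−5)/100 = 75%. So the untimed breakdown cannot stand in for that figure either.

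**3. The breakdown limited to escape treatment before the 12-month biopsy.** Let e be non-CR patients who had escape treatment before that biopsy. Then CR without escape = (80−k)/(100−k−e), and CR with escape = k/(k+e).

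- k = 3, e = 0: 77/97 = 79.4% and 3/3.
- k = 3, e = 5: 77/92 = 83.7% and 3/8 = 37.5%.

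The time limit removes most of the distortion but not all of it. ESCC before month 12 is both a failure and a trigger for escape treatment, so e need not be zero. The breakdown should therefore be read as counts, not as a comparison of rates.

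**4. The supportive 12-month figure.** This is (CR count − k)/n. One patient is 1.0 point at n = 100, or 1/80 = 1.25 points if the per-protocol set were 80. Exact 95% intervals at n = 100:

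| Counted CR | k | Supportive CR (95% CI) |
|---|---|---|
| 80 | 0 | 80% (70.8–87.3) |
| 80 | 3 | 77% (67.5–84.8) |
| 80 | 5 | 75% (65.3–83.1) |
| 80 | 10 | 70% (60.0–78.8) |
| 90 | 0 | 90% (82.4–95.1) |
| 90 | 5 | 85% (76.5–91.4) |

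The shift equals the planned half-width only at about k = 6 to 8.

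**5. Is k given anywhere?** No. The earlier study in CIP 6.2 is not a usable guide. It covers later follow-up, states 7 recurrences but itemises only 6 by grade (5+1) and by treatment (5+1), and has one pathology result pending. Its count of patients treated by ESD without ESCC would be 2 or 3 of 78, and not for the first 12 months.

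**The case against.** The strongest case is that nothing here is an error. The success rule is stated consistently in two places, and patients must still be free of MGIN or worse in TA biopsies at 12 months. The group is small and may be empty. This stands, and it is why the point is minor.

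Nor is it certain that every 12-month non-responder would be coded as an escape user. The definition in CIP 9.10 is narrower: ESCC in biopsies, non-flat lesions, or lesions otherwise suspicious for ESCC. Table 2 also puts the two uses in separate rows, one for ESCC or suspicious disease (3, 6 and 9 months and follow-up) and one for residual ESCN (from month 12). This too stands. The 80/80 against 0/20 result follows from CIP 9.4.1 and 9.4.3 as written, but a programmer working from CIP 9.10 could build a different variable. The sections need reconciling for the analysis, and an analysis variable open to two readings needs a definition in any case.

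A reader might also infer that the sponsor deliberately dropped the breakdown from the SAP. The documents do not support that. The SAP was written for CIP v4, while the CIP in hand is v7.0, so the omission may be no more than version lag.

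Finally, CIP 13.3 and SAP 7.1.3 allow further subset analyses. They do so permissively and name none on this question.

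**Conclusion.** The concern holds as a minor one, in two parts. The breakdown by escape treatment in CIP 13.6 has no time window and can sort patients by the endpoint. Under the reading in CIP 9.4.1 and 9.4.3 that distortion is complete and does not depend on any early resection. And no planned analysis shows the 12-month CR reached without resection. That part is worth 1 point per affected patient at n = 100, for an unknown number who may be none.

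A reader might go further and conclude that the primary CR is invalid, or inflated by RFA failures rescued with surgery or resection. The documents do not support this. Persistent MGIN or worse after four sessions, residual ESCN at 12 months, ESCC and non-endoscopic therapy already count as failures. The primary result is valid for RFA with endoscopic rescue. Nor does a resection prove that RFA failed, since "the Investigator can perform escape treatment if deemed necessary, regardless of the biopsy result". The plan reports the primary endpoint as a rate with a 95% CI, and no pass/fail decision changes.

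The figures in steps 2 to 4 rest on assumed values of k, L and e and on illustrative CR counts of 80 and 90.

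**What to change.** Keep the primary endpoint and all clinical rules.

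1. **CIP 13.6, carried into SAP 7.11.** Take escape treatment out of the list of confounding factors. Limit the breakdown to escape treatment given before the 12-month biopsy. Present it as descriptive counts by reason and by specimen histology (LGIN or less, MGIN, HGIN, ESCC). State which indications the variable covers, since CIP 9.10 and 9.4.3 differ.

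2. **SAP 7.9.1 and CIP 13.4.** Add one supportive row, in the same per-protocol set and on the same 12-month biopsies as the primary analysis. Any EMR, ESD or non-endoscopic therapy in the TA before the 12-month biopsy counts as non-response. Report it with a 95% CI beside the primary result, labelled a conservative lower bound for CR by RFA alone. It is a lower bound because some resected lesions may not be neoplastic.

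The cost is one extra table. For endoscopic escape treatment the histology is already collected: "For patients who undergo endoscopic treatment, final pathology is required". The supportive figure will be equal to or lower than the primary one. If the count is zero, the table shows that rescue played no part in the result. Specifying it now avoids a post hoc choice.
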